15.3 PEDIATRIC QUALITY OF LIFE INVENTORY (PEDSQL)

15.4 GUIDELINES AND DEFINITIONS FOR RECORDING ADVERSE EVENTS

The Principal Investigator or a designated member of his/her staff will probe each subject for any AEs that may have occurred. The Investigator should always ask the same question when conducting the verbal probe in order to ensure uniformity between subjects. The Investigator should ask:

"How are you doing (feeling)?"

Based on the subject's response to this question, the Investigator should ask additional questions relevant to the specific complaint such as:

"How severe is/was the symptom?"

"How often did the symptom occur?"

"How long did the symptom last?"

It is the Investigator's responsibility to review the results of all diagnostic and laboratory tests as they become available and ascertain if there is a clinically significant change from baseline. If the results are determined to be a clinically significant change from baseline, this should be reported as an AE. The Investigator may repeat the diagnostic procedure or laboratory test or request additional tests to verify the results of the original tests. When possible, a diagnosis associated with the abnormality should be used as the reported AE.

Using provided definitions, the Investigator will then:

- (1) rate the intensity and seriousness of the AE,
- (2) estimate the causality of the AE to oral treprostinil (study drug), and
- (3) note actions taken to counteract the AE.

Definitions of Intensity, Seriousness, Causality, Action Taken, and Outcome

INTENSITY

An assessment of the relative intensity (severity) of an AE is based on the Investigator's clinical judgment. The maximum intensity encountered during the evaluation period should be checked. The assessment of intensity should be independent of the assessment of the seriousness of the AE.

SERIOUSNESS

A serious AE is one that represents an actual or potential significant hazard. This includes, but is not limited to, an event that is fatal, life-threatening, permanently or severely disabling, requires or prolongs inpatient hospitalization, is a congenital abnormality (offspring of subject) or is medically significant (important medical events that may not result in death, be life-threatening, or require hospitalization may be considered a serious AE when, based upon appropriate medical judgment, they may jeopardize the subject and may require medical or surgical intervention to prevent one of the outcomes listed in this definition).

Hospitalizations that would not be considered SAEs include those for:

- Routine treatment or monitoring of the study indication not associated with any deterioration in condition (e.g., hospitalization for a routine RHC).
- Treatment which was elective or pre-planned, for a pre-existing condition not associated with any deterioration in condition (e.g., pre-planned operation which does not lead to further complications etc.).
- Treatment of an emergency, in an outpatient setting for an event not fulfilling any of the definitions of serious as given above and not resulting in hospital admission.

CAUSALITY

An estimate of causality between a specified AE and the study drug is made by the Investigator. Several factors should be considered when determining causality. These factors include temporal relationship and response to withdrawal or reintroduction of the study drug. Definitions of the causality categories are as follows:

- NOT RELATED there is not a temporal relationship to study drug administration (too early, or late, or study drug not taken), or there is a reasonable causal relationship between another drug, or concurrent disease and the SAE, or any of the following:
 - An event that precedes the first administration of the study drug
 - An event for which the cause is clearly related to an external event;
 - Temporal relationship to study drug is atypical
 - Is readily explained by an intercurrent illness AND has an expected level of severity, duration, and resolution
 - An alternative explanation (concomitant drug, intercurrent illness) is likely.
- POSSIBLE there is a reasonable causal relationship between the study drug and the SAE. Dechallenge information is lacking or unclear- study drug administration was not modified in response to the SAE, or any of the following:
 - Has a reasonable temporal relationship to study drug
 - The event has a plausible biological link to the activity of the study drug
 - Is unlikely to be related to an intercurrent illness or has an unexpected degree of severity, duration or complication
 - Unlikely due to an alternative illness or external event (e.g. surgical procedure, accident)
- PROBABLE there is a reasonable causal relationship between the study drug and the SAE. The event responds to dechallenge- the event resolves or improves with modification of study drug administration. Rechallenge (the original study drug dose was not restarted) is not required or any of the following:
 - Has a reasonable temporal relationship to study drug
 - The event has a plausible biological link to the activity of the study drug
 - Not readily explained by an intercurrent illness
 - Not readily explained by external event
 - Improves on discontinuation of study drug
 - If study drug had been discontinued, may recur on reintroduction of study drug

ACTION TAKEN

STUDY DRUG DOSE MODIFICATION*

- Dose Not Changed the dose or regimen of the study drug was not changed.
- Drug Interrupted administration of the study drug was stopped temporarily.
- Drug Withdrawn administration of the study drug was stopped permanently and not restarted.
- Unknown changes to the administration of the study drug cannot be determined.
- Not Applicable

*NOTE: Only the last study drug action should be recorded in the eCRF. For example, if the study drug is withdrawn and then the decision is made to restart, the dose modification of "Drug interrupted" should be reported on the SAE form.

OUTCOME

- Fatal The study subject died.
- Not Recovered / Not Resolved The AE was ongoing at the time of death or at the time the subject was lost to follow up.
- Recovered / Resolved The AE resolved.
- Recovered / Resolved with Sequelae The AE is considered resolved however there is a residual sequelae. Some events do not return to baseline, such as metastasis or progression of disease; however, once these events are determined by the Investigator to be stable or chronic, the Investigator may consider the event to be resolved or resolved with sequelae.
- Recovering / Resolving The AE is improving but is not yet completely recovered/resolved.
- Unknown The outcome of the AE cannot be determined.

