	All subjects must be optimally treated (as determined by the Investigator) with background PAH therapies (e.g., phosphodiesterase type 5 inhibitor [PDE-5i], endothelin receptor antagonist [ERA], soluble guanylate cyclase [sGC]) for at least 90 days and have been on a stable dose without changes (except documented weight based adjustments) for at least 30 days prior to the first dose of oral treprostinil.
	 Cohort 1: Remodulin to Oral Treprostinil Transition Subjects must have been receiving IV/SC Remodulin for at least 90 days and at a stable dose for at least 30 days prior to the first dose of oral treprostinil. The IV/SC Remodulin dose will be between 25-75 ng/kg/min, inclusive, for the first five subjects enrolled in Cohort 1. Following a safety review by the Data Safety Monitoring Board (DSMB) after the first five Cohort 1 subjects have been enrolled and transitioned to oral treprostinil (study drug), the dose range may be expanded to 25-125 ng/kg/min, inclusive, for the remaining subjects.
	Cohort 2: Inhaled Prostacyclin to Oral Treprostinil Transition Subjects must have been receiving inhaled prostacyclin therapy for at least 90 days and at a stable dose for at least 30 days prior to the first dose of oral treprostinil.
	Cohort 3: Add-On to Current PAH Therapy in De Novo Prostacyclin Subjects must weigh at least 22 kg.

Drug Dosage and	All Cohorts:
Formulation	All subjects will receive study drug (oral treprostinil extended release tablets). The tablets may be provided as 0.125, 0.25, 1, or
	2.5 mg strengths. Oral treprostinil will be dosed three times daily (TID) or four times daily (QID) at the discretion of the Investigator, with food. Dosing will take place approximately every 6 to 8 hours for TID dosing, or approximately every 4 to 6 hours for QID dosing, with adjustments permitted based on the subject's lifestyle and schedule. Sudden dose escalation or reductions should be avoided as they may lead to intolerable adverse events (AEs) or worsening of PAH. Gradual dose titrations are recommended to reduce the risk to subjects.

Cohort 1: IV/SC Remodulin to Oral Treprostinil Transition

Dose Transition Schedule:

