### 11.3 ADVERSE EVENTS

The AEs are collected from the time the informed consent form is signed until study termination. There are a number of AEs that are considered expected events given the underlying disease of study, PAH. These expected events attributable to PAH were not

recorded as an AE unless the event was serious or unusual with respect to intensity, frequency, or duration, or there was a reasonable possibility that it may have been caused by the study drug.

Adverse events will be coded using MedDRA PTs and SOC. All AEs reported in the eCRF will be listed, including non-treatment-emergent and treatment-emergent events.

Non-treatment-emergent AEs are defined as those AEs starting prior to the date of first oral treprostinil dosing. Treatment-emergent adverse events (TEAEs) are defined as those AEs starting on or after the date of first oral treprostinil dosing. The listing will include cohort, subject number, verbatim term, PT, SOC, treatment-emergent status, start/stop date, seriousness, severity, frequency, relationship to oral treprostinil, action taken with oral treprostinil, relationship to background medication, action taken with background medication, and outcome.

The TEAEs will be summarized first in an overall summary, which includes the number of subjects with at least 1 TEAE, at least 1 oral treprostinil attributable TEAE, at least 1 serious TEAE, at least 1 TEAE leading to oral treprostinil discontinuation, at least one background therapy attributable TEAE, at least one TEAE leading to background therapy discontinuation, and any fatal TEAEs. The overall summaries will also include the number of events for each of these categories.

Non-treatment-emergent AEs will be summarized by cohort using PTs. The PTs will be sorted by decreasing overall frequency.

The TEAEs and serious TEAEs will be summarized by cohort using SOC/PT and PT, separately. The summaries will include the number and percentage of subjects reporting and the number of events reported for each SOC/PT and each PT, respectively, for each cohort, in order of decreasing overall frequency, both within SOC and PT.

The TEAEs will be summarized by severity within PT. The TEAEs and serious TEAEs considered attributable to oral treprostinil will be summarized by SOC/PT and PT, as

described above. The TEAEs leading to oral treprostinil discontinuation will be summarized by PT.

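### The AE action-taken list has no option for a reduced dose and the SAP tabulates only discontinuations, so AE-driven dose reductions are miscoded, not summarised, and can only be inferred from dates

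*Protocol*

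**What the plan says.** Protocol 15.4, under Action Taken, lists five codes for study drug dose modification. The first is defined as "Dose Not Changed the dose or regimen of the study drug was not changed". The next two are a temporary stop ("administration of the study drug was stopped temporarily") and a permanent one ("administration of the study drug was stopped permanently and not restarted"). The fourth is for cases where "changes to the administration of the study drug cannot be determined". The fifth, not applicable, has no definition. The note below the list reads "Only the last study drug action should be recorded in the eCRF". Its example is a drug withdrawn and later restarted, which is to be reported as interrupted.

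Dose reductions are foreseen. The synopsis warns: "Sudden dose escalation or reductions should be avoided as they may lead to intolerable adverse events". Protocol 6.1.1 to 6.1.3 repeat the caution and have sites contact families between visits both to monitor AEs and to decide on titration. The same sections require every change of oral treprostinil dose to be entered in the eCRF.

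SAP 11.3 puts action taken with oral treprostinil into the AE listing. For summaries by action on study drug it goes no further than discontinuation: "The TEAEs leading to oral treprostinil discontinuation will be summarized" by preferred term, plus a discontinuation line in the overall AE summary. The table list in SAP 13.1 has nothing for reduction or interruption. SAP 11.1 lists dose changes with a start date and the morning, midday and evening doses.

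**The concern.** The primary objective in both documents is safety and tolerability of a drug whose dose is adjusted to the individual child. An AE that leads to a lower dose is a tolerability outcome short of withdrawal, and the action-taken field is where a reader would look for it.

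The field cannot hold it. The primary endpoint does not show it either: success means being clinically maintained on oral treprostinil through Week 24 (Protocol 10.3.1, SAP 10.1), with no dose condition stated. A child whose dose was cut because of AEs can therefore count as a success, with nothing in the AE tables to show the cut.

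Causality coding is also affected. Protocol 15.4 separates probable from possible partly by whether the event improved after study drug administration was modified. The field beside that judgement cannot record one of the main kinds of modification.

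**Working it through.** No sample size, power or event figure is involved, and the plan states no number to reproduce. The check sets the coding rule, the planned outputs and the dosing data side by side.

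**Step 1. Does any code fit a lowered dose?** Take an AE after which the dose is lowered and dosing continues.

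| Code in Protocol 15.4 | Definition | True of a lowered dose? |
|---|---|---|
| Dose not changed | "the dose or regimen of the study drug was not changed" | No, it was changed |
| Interrupted | "administration of the study drug was stopped temporarily" | No, dosing continued |
| Withdrawn | "administration of the study drug was stopped permanently and not restarted" | No, dosing continued |
| Unknown | "changes to the administration of the study drug cannot be determined" | No, the change is known |
| Not applicable | none given | No, an action was taken |

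The first four are false by their own definitions, and the fifth is no description of what happened. A dose held at its current level is different: it fits the first code.

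**Step 2. What does the last-action rule do?** With the present list it does little harm, because a reduction cannot be entered at all, and its own example gives the right final status. It would matter once a reduction code exists. An AE handled first by a reduction and then by an interruption would keep only the interruption.

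**Step 3. Can the dosing data stand in?** Partly. Dose changes have start dates (SAP 11.1) and AEs have start and stop dates (SAP 11.3), so a decrease that overlaps an AE can be found. The dosing listing, however, names no reason for a change and no linked AE.

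The SAP's dose measure adds a second difficulty. SAP 11.1 defines oral dose as the sum of a day's doses divided by the number of doses that day. Protocol 6.1 allows a switch from TID to QID and gives six examples. For each:

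- change per dose = (QID dose − TID dose) / TID dose
- change in daily total = (4 × QID dose − 3 × TID dose) / (3 × TID dose)

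| TID to QID dose (mg) | Change per dose | Daily total (mg) | Change in daily total |
|---|---|---|---|
| 1.75 to 1.25 | −28.6% | 5.25 to 5 | −4.8% |
| 2.5 to 1.875 | −25.0% | 7.5 to 7.5 | 0% |
| 3.75 to 2.75 | −26.7% | 11.25 to 11 | −2.2% |
| 5.5 to 4.125 | −25.0% | 16.5 to 16.5 | 0% |
| 8.25 to 6.125 | −25.8% | 24.75 to 24.5 | −1.0% |
| 10 to 7.5 | −25.0% | 30 to 30 | 0% |

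On the SAP measure a change of frequency looks like a 25% to 29% dose reduction, while total daily dose falls by 0% to 5%. Real reductions and frequency switches cannot be told apart on that measure alone.

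**Step 4. Would summing the listed doses help?** Only if all four QID doses are there. The listing names three slots. If a fourth dose were left out, the second example would sum to 3 × 1.875 = 5.625 mg against 7.5 mg, again an apparent fall of 25%. Whether the eCRF holds a fourth slot is not stated, so this is conditional.

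**The case against.** A reader might infer that AE-driven reductions cannot be reported at all, or that the reportable count is zero whatever happened. The documents do not support that. Dose changes in every cohort go into the eCRF, they are listed with dates, individual doses are plotted over time, and the SAP preface allows further analyses to be documented in the CSR. What is missing is direct attribution and a planned summary.

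A reader might also infer that reduction is the usual or most frequent response to an AE here. Neither document says so. They show only that reductions are foreseen.

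The strongest objection is that Appendix 15.4 is not the eCRF. The SAP's AE listing includes frequency and action taken with background medication, which 15.4 does not define, so the eCRF evidently holds more than the appendix shows. It may have a reduction code or a reason for each dose change. This stands, and it is why confirming the code list comes first. It does not supply the missing SAP table.

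It is also fair that the primary endpoint does not use this field, that TEAEs are summarised by severity, seriousness and attribution, and that the study is descriptive. These points limit the consequence. They do not make a code true when its definition is false.

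**Conclusion.** The point holds in limited form. As Protocol 15.4 is written, an AE managed by lowering the dose has no correct action code, and the SAP plans no summary of AEs leading to reduction or interruption. Such reductions can be inferred by matching dates, but no reason for change is named and the SAP's dose measure turns a TID-to-QID switch into an apparent 25% to 29% reduction.

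The number of AEs affected cannot be derived from the documents. The percentages come from the protocol's six example switches and show how the measure behaves; they do not estimate how often it misleads. The success percentages and the discontinuation table are unaffected.

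The conclusion assumes that the eCRF follows the appendix list and that the list is complete as printed. If the eCRF already has a reduction code, the coding fault falls away and the missing summary remains. Because tolerability is the primary objective and the remedy is cheap, the change should be made.

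**What to change.** - Confirm the eCRF code list for action taken with study drug. If it matches Protocol 15.4, add dose reduced and dose increased to both.
- Keep the last-action rule for deciding between interrupted and withdrawn, where it works. Record any dose reduction for the AE separately, or keep all actions, so that a later action does not overwrite it. Switching to the most severe action would be worse: a drug withdrawn and then restarted would stay coded as withdrawn and inflate the discontinuation table.
- Add one SAP table of TEAEs leading to dose reduction or interruption, by preferred term and cohort.
- For data already collected, add a listing of decreases in total daily dose that overlap a TEAE, labelled as inferred. Use total daily dose, not dose per administration, and include all four doses for subjects on QID.

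The cost is a small eCRF update, some queries on AEs already entered, one extra table and one extra listing, for up to 40 subjects.

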15.5 PHARMACOKINETIC SAMPLE PROCESSING

Collection, Processing and Shipment of Plasma Specimens

Cohort 1: A total of 8 approximately 3 mL blood specimens (approximately 24 mL) for PK analysis will be collected from each subject during the study. Pharmacokinetic samples will be collected at Baseline and Week 24.

Cohorts 2 and 3: A total of 5 approximately 3 mL blood specimens (approximately 15 mL) for PK analysis will be collected from each subject during the study. Pharmacokinetic samples will be collected at Week 24 only.

Pharmacokinetic Specimen Collection

Collection may occur by venipuncture or cannula with a saline lock; the use of heparin is not permitted.

Cohort 1: The Baseline PK sampling will begin with a time 0 sample and the following subsequent time points: 4 and 8 hours after time 0. At Baseline, time 0 should be at the same time of the day that it is estimated the Week 24 oral treprostinil (study drug) dose will occur.

All Cohorts: No oral treprostinil dose changes are allowed within five days of the Week 24 PK sampling, unless required to protect subject safety. All subjects on a TID dosing regimen will undergo the Week 24 PK assessment based on the first daily dose (morning dose) of oral treprostinil. If a subject is on a QID dosing regimen, the Investigator may conduct the PK assessment based on the first daily dose (morning dose) or the second daily dose (midday dose) at their discretion. The PK assessment dose of study drug at Week 24 should occur approximately 8 hours after the prior evening's last dose of oral treprostinil for subjects using the morning dose of study drug should occur 4 to 6 hours after that day's morning dose. The Week 24 PK sampling will begin with a pre-dose sample (immediately prior [i.e., 10 minutes ± 5 minutes] to the administration of the PK assessment oral treprostinil [study drug] dose), and the following subsequent time points: 2, 4, 6, and 8 hours after the PK assessment dose

of study drug (all time points will be based off of the time the PK assessment dose of study drug is administered).

If the subject is on a TID regimen, no other doses of oral treprostinil should be taken during the PK sampling period; subjects should take their next dose of oral treprostinil (midday dose) after the final 8-hour PK sample is collected.

If the subject is on a QID regimen, the subject will take their next daily dose (midday dose or early evening [PM #1] based on timing of PK assessment dose) between the 4 and 6 hour time points of the PK sampling (± 10 minutes) with food, based on the subjects typical dosing schedule.

Samples should be drawn within a ± 10 minute window from their scheduled time point. Record the time and reason for late blood draws in the eCRF. Hemolyzed blood samples may be redrawn. Indicate hemolyzed sample in the eCRF.

Specimen Processing

- Collect approximately a 3 mL blood specimen in an evacuated glass tube containing
 K₃-EDTA as an anticoagulant and immediately place the specimen on ice.
- Within 1 hour of collection, centrifuge the specimen at 4 °C for 10-15 minutes at 3000 g.
- Label the shipping tube with the subject number, treatment, and specimen collection time and date.
- Pipette approximately 1 mL plasma into a shipping tube. Pipette the remainder of the plasma into a second, identically labeled tube for use as a backup specimen.
- Freeze samples immediately at -20 to -25°C. The 1 mL sample will be transported on dry ice to the Sponsor-designated laboratory for analysis. The remainder sample will be retained at the site and transported later in the event of an emergency or if deemed necessary by the Sponsor.

Shipping Procedures

- All shipments must be accompanied by a packing list. Please note on the packing list any specimens that are hemolyzed.
- Package the shipping tubes to prevent breakage and contamination in Styrofoam boxes containing a generous supply of dry ice that will allow for 3 days in transit.
- Prior to the shipment of specimens, contact the Sponsor and the bioanalytical laboratory by phone and fax or email. An advanced electronic copy of the packing list should also be provided to the laboratory.
- Samples should be shipped overnight to the bioanalytical laboratory, on dry ice, on a Monday, Tuesday, or Wednesday.
